c. Treatment assignment and randomization. All study participants will receive the same treatment procedures. No assignment or randomization is required.

V. STUDY PROCEDURES

a. Study visits and parameters to be measured: Participants will have the option to participate at the MGH IHP, at their home, or via Enterprise Zoom.

Once participants are consented, the typical study sequences include (*also in Figure 1*): Each step is described in additional detail in the section that follows.

- 1) Pre-treatment: Completion of pre-treatment cognitive-linguistic assessments, naming probes, and spontaneous speech probes (sessions approximately 2 hours in length over an average of 3-5 days to mitigate any effect of fatigue on assessment performance).
- 2) During Treatment: Participation in the treatment for a period of eight weeks. All participants will receive the same treatment. Participants will receive in-person therapy at the MGH Institute of Health Professions, home visits, or virtual sessions (via Zoom). Participants will attend three 70-minute treatment sessions per week for eight consecutive weeks. Treatment sessions will be conducted by a certified SLP. Starting on Week 2, the first treatment session of each week will begin with a 30-minute assessment, consisting of a naming probe, a connected speech probe, and a strategy knowledge probe, in which the participant will be asked to provide the six strategy components. Treatment will stop at the end of the eight weeks, or after three consecutive naming probe performances over 90% accuracy, whichever occurs first.
- Post-treatment re-administration of assessments: Participants will complete the same cognitive-linguistic assessments, naming probes and spontaneous speech probes as they did pre-treatment within 20-30 days following the last treatment session. Sessions will last approximately 2 hours in length over an average of 3-5 days.
- 4) Post-treatment tests of retention: Participants will attend two additional post-treatment sessions one month and two months after the final treatment session. During each post-treatment session, participants will complete a 176-item naming assessment, one connected speech probe, and a strategy knowledge probe.

Phase 1) Pre-treatment:

a) Cognitive-linguistic assessments. Eligible and consented participants will complete a battery of standardized cognitive-linguistic assessment, including:

- The Western Aphasia Battery-Revised (WAB-R)⁴⁶,

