- General Health Questionnaire-12³⁵,
- Stroke and Aphasia Quality of Life Scale⁴¹,
- Subtests of the Cognitive Linguistic Quick Test-Plus (CLQT+)³⁹,
- The Metalanguage in Aphasia Assessment⁴⁰ (MetAphAs),
- The Communication Confidence Rating Scale for Aphasia (CCRSA),
- The Scenario Test⁸⁶

All assessments will be administered via paper and pencil, unless the participant is participating remotely. If they participate remotely, a fully encrypted device will be utilized but all responses will still be collected via paper and pencil.

b) Naming assessments and connected speech probes: Participants will complete three pretreatment naming assessments to establish a stable baseline⁸³ (*Figure 1*). During each baseline session, participants will complete a 176-item naming assessment and one connected speech probe. The 176-item naming assessment has objects from eight categories: animals, clothing, fruits and vegetables, occupations, household objects, other foods, tools. and transportation^{37,45,51}. Participants will be asked to name each object. To elicit connected speech, we will ask participants to verbally describe a picture, weekly activity, and/or personal memory (e.g., Tell me all about your weekend). Naming assessment and connected speech probe coding: We will calculate naming accuracy from the naming assessments and transcribe participants' prenaming verbalizations in order to later analyze and characterize their pre-treatment naming attempts. We will also transcribe and analyze participants' connected speech samples using Correct Information Unit (CIU) analysis⁶⁴, which provides measures of communicative efficiency and informativeness. Treatment and naming probe object selection: Participants' performance on the three pre-treatment naming assessments will determine which objects are either: trained during treatment, included in weekly naming probes, or untrained and used to test for deneralization post-treatment. Any objects a participant is unable to name on one, two, or three assessments will be included in the participant's object list. Of the included objects, we will create separate treatment and naming probe object lists taking into account the objects' semantic category and complexity.

Phase 2: Treatment

Each treatment session will have three sections:

- Strategy Education (~ 15 minutes),
- Naming Treatment Plus Strategy Application (~40 minutes),
- Strategy Debrief (~15 minutes).

Strategy Education. The clinician will:

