Phase 4 post-treatment tests of retention: Participants will attend two additional post-treatment sessions one month and two months after treatment completion to evaluate retention. During these study visits, participants will complete naming assessment and a connected speech connected speech task in which we will ask participants to verbally describe a picture, weekly activity, or personal memory description (e.g., *Tell me all about your weekend*).

- b. Drugs to be used: N/A
- c. Devices to be used: N/A
- d. Procedures/surgical interventions: N/A

e. Data to be collected and when data is to be collected

Pre- and post-treatment data: All pre-treatment and post-treatment cognitive-linguistic assessment data will be collected during pre- and post-treatment assessment sessions. This data will be collected on each respective assessment material's proper test booklet. Data from pre- and post-treatment naming probes will include naming accuracy and circumlocution attempts (i.e., naming attempts). Data from pre- and post-treatment spontaneous speech probes will include verbatim transcriptions of each participant's responses to the spontaneous speech probes (e.g., *Tell me all about your weekend*). Naming and spontaneous speech probe data will be collected

during the three pre-treatment and six post-treatment sessions. Audio recordings of naming probes will be randomized and coded for accuracy.

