During treatment data: During treatment, we will collect treatment session data and weekly probe data. Weekly probe data will be the exact same as the pre- and post-treatment naming and spontaneous speech probe data (naming accuracy, circumlocution attempts, verbatim transcriptions), in addition to strategy knowledge data probes (i.e., asking participants to identify as many of the six strategy components as possible). These weekly probes will occur once per week for the eight weeks of treatment. During the Strategy Education section of treatment, data will include quantification of strategy component knowledge (out of a possible six). During the Naming Treatment Plus Strategy Application section of treatment, data will include: Percent of items participant correctly identified whether they would be able to name the object before attempting to name it, naming accuracy before feature generation, number of features generated by the participant per item, number of correctly matched features with feature types per item, number of additionally identified feature types per item, and naming accuracy after feature generation. During the Strategy Debrief section of treatment, data will include: transcription of participant's reaction and opinion of treatment session and number of home-based opportunities identified by the participant in which they could use the strategy.

VI. BIOSTATISTICAL ANALYSIS

a. Specific data variables being collected for the study.

Cognitive-linguistic assessments (pre-treatment and post-treatment): Language and cognitive assessments will be scored based on standardized norms and methods of administration and scoring provided in testing manuals. Cognitive-linguistic assessments and inperson treatment sessions will be videotaped to provide a measure of reliability of scoring and administration of assessments and treatment.

Naming, spontaneous speech, and strategy knowledge probes (pre-treatment, during treatment, and post-treatment): We will collect (1) naming accuracy, (2) verbatim pre-naming verbal naming attempts, (3) verbatim responses to spontaneous speech probes, and (4) number of identified strategy components.

Treatment data: We will collect data on: (1) number of identified strategy components and (2) number of feature words during moments of naming difficulty.

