Aim 1b. Determine whether PWA learn the strategy and consequently demonstrate a change in their language behavior in moments of naming difficulty. Analyses: We will use visual inspection to examine participants' identification of the strategy components from Treatment Week 2, to Week 8, to post-treatment sessions. We will calculate effect sizes to measure the effect of treatment on the total number of feature words produced during naming assessments and on the average number of feature words produced per naming attempt during assessments, from pre- to post-treatment. Hypotheses: We expect that strategy training will result in participants' ability to identify all six strategy components by Week 8 and at least four of the strategy components during maintenance/retention sessions. We also hypothesize that strategy training will lead PWA to produce more feature words (i.e., engage in circumlocution) during moments of naming difficulty. Specifically, we expect to find medium to large effects on the number of feature words PWA produce during naming attempts.

Aim 2. Evaluate the effect of strategy training on patients' language production during connected speech. Statistical Analyses: We will calculate effect sizes to measure the effect of treatment on number of object words, feature words, CIUs, and CIUs/minute participants produce during connected speech tasks. Hypotheses: We hypothesize that strategy training will lead PWA to produce more object and feature words during connected speech. We expect medium to large effects on object words, feature words, CIUs, and CIUs/minute during connected speech from pre- to post-treatment.

Additional analyses: We will create mixed-effects models using treatment-phase data (e.g., strategy component identification) as fixed effects, and pre-treatment cognitive-linguistic measures (e.g., CLQT+ results) and participant characteristics (e.g., aphasia severity) as random effects to further understand post-treatment outcomes. We will calculate normalized change scores to measure participants' overall improvement relative to their baseline performance and maximum possible change⁵⁶. We will report changes between participants' pre- and post-treatment WAB-R Aphasia Quotient⁴⁶ scores using the benchmarks proposed by Gilmore and colleagues³³.

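### Random-order coding is stated only for naming accuracy; the plan states no masking to phase for the connected-speech counts of Aim 2 and leaves the feature-word counts of Aim 1b unclear

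*Combined protocol and SAP*

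**What the plan says.** Section V.e (Data to be collected), under the pre- and post-treatment data, lists naming accuracy and circumlocution attempts from the naming probes, and verbatim transcripts from the spontaneous speech probes. It ends: "Audio recordings of naming probes will be randomized and coded for accuracy".

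For connected speech, section V.a, Phase 1(b), says that staff will "transcribe and analyze participants' connected speech samples using Correct Information Unit (CIU) analysis". For naming attempts, the same paragraph says that they will "transcribe participants' prenaming verbalizations in order to later analyze and characterize their pre-treatment naming attempts". Neither statement mentions coding order, masking or who codes.

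Section VI.c bases Aim 1b partly on the "total number of feature words produced during naming assessments" and on the average per naming attempt. It bases Aim 2 on the "number of object words, feature words, CIUs, and CIUs/minute participants produce during connected speech tasks". Both aims expect more of these words after treatment, with medium to large effects.

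On allocation, section IV.c says: "All study participants will receive the same treatment procedures. No assignment or randomization is required".

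On reliability, section VI.a says: "Cognitive-linguistic assessments and inperson treatment sessions will be videotaped to provide a measure of reliability of scoring". That sentence concerns the standardized battery and the treatment sessions. The naming and spontaneous speech probes have their own paragraph in VI.a, with no such check.

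**The concern.** Counting CIUs, object words and feature words means deciding, word by word, what qualifies. A coder who knows that a sample is post-treatment also knows which way the hypothesis points, and borderline words may then be resolved in that direction. Every participant is treated, so no comparison arm shares the shift and subtracts it. A shift at the boundary between phases looks the same as a treatment effect, both in the effect size and in the visual inspection planned in VI.c.

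All of Aim 2 and the feature-word part of Aim 1b are at stake. The plan already uses random order for one outcome, so what is missing is the extension of a safeguard that the sponsor has itself adopted.

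**Working it through.** **1. What is covered, outcome by outcome**

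| Outcome | Source | Random order stated? |
|---|---|---|
| Naming accuracy (Aim 1a) | naming-probe audio | yes (V.e) |
| Feature words in naming (Aim 1b) | transcribed attempts from naming assessments | unclear: same recordings, but the stated purpose is accuracy |
| Object words, feature words, CIUs, CIUs/minute (Aim 2) | connected-speech transcripts | no |

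The identification codes in VII.a and IX.b protect privacy. They are not said to hide the phase. Even for naming accuracy, random order is not the same as a statement that coders are masked.

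**2. How a coding shift enters the planned effect size**

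The plan gives no figure that depends on masking, so there is none to reproduce. The effect size in VI.c is

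d = (mean post − mean pre) / SD_pre,

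with SD_pre the participant's own pre-treatment SD. If post-treatment samples are coded higher by a constant b, the result is d + b / SD_pre. The design has no term that removes it.

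**3. Illustration under assumed values**

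Inputs from the plan: 3 pre-treatment and 6 post-treatment probe sessions (V.e).

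Assumed: independent normal session scores with SD σ, no true change, b = 0.25σ to 1.0σ, and d > 0.5 as a marker, because the plan does not define a medium effect in numbers.

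Three baselines leave SD_pre with ν = 2 degrees of freedom:

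E[1/SD_pre] = √(ν/2) · Γ((ν−1)/2) / Γ(ν/2) / σ = Γ(0.5) / Γ(1) / σ = √π / σ = 1.77/σ.

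The mean addition to d is therefore 0.25 × 1.77 = 0.44, 0.5 × 1.77 = 0.89, or 1.0 × 1.77 = 1.77. Medians and shares come from 400,000 simulated participants per row:

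| Shift b | Mean added to d | Median d | Share d > 0.5, 6 post sessions | Share d > 0.5, 3 post sessions |
|---|---|---|---|---|
| 0 | 0 | 0 | 27.4% | 30.2% |
| 0.25σ | 0.44 | 0.28 | 39.9% | 41.1% |
| 0.5σ | 0.89 | 0.57 | 53.2% | 52.7% |
| 1.0σ | 1.77 | 1.15 | 77.3% | 74.4% |

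The first row shows that more than a quarter of participants pass 0.5 from noise alone, because SD_pre rests on three values. Only the rise above that row belongs to the coding shift: with 6 post sessions, 53.2 − 27.4 = 25.8 percentage points at b = 0.5σ.

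**4. Which scores cannot wait for shuffled coding**

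- The initial naming score decides eligibility (III.a).
- The three baseline naming assessments decide the object lists (V.a, Phase 1(b)).
- Weekly naming accuracy feeds the stopping criterion (V.a, item 2).

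None of these uses CIUs, object words or feature words, so delaying that coding holds up no decision in the study.

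**The case against.** The strongest reply is that the plan is silent here, and silence is not evidence of unmasked coding. This stands. A reader might infer that the Aim 1b and Aim 2 outcomes will be coded with the phase in view and that the results will be biased. No section says so. The most the text supports is that masking is not stated and that bias is possible.

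Second, the Aim 1b feature words come from the naming assessments, and V.e lists circumlocution attempts among the naming-probe data just before the randomization sentence. The same shuffled recordings may be used for both. This also stands, so Aim 1b is a point to clarify rather than a plain gap. For Aim 2 no such reading is available.

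Third, connected speech is transcribed verbatim and scored by a cited published system, recordings are kept for seven years (VII.a), and speech responses are to go to a shared database (section IX). Masked recoding would be possible later. This stands only in part, because no such recoding is planned. The rules and reliability of the scoring system cannot be judged from these documents, so no claim is made that CIUs need more judgement than naming accuracy.

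Fourth, masking would be imperfect. Talk about the week's activities, or open use of the taught strategy, can reveal the phase, and participants may decline recording (IV.b). Both limits are real and are carried into the fix.

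**Conclusion.** The point holds in a limited form. The plan's only masking-type step is tied to naming accuracy. For Aim 2 no random order or masking to phase is stated, and for the Aim 1b feature words the coverage is unclear. Because these are judged counts in an uncontrolled pre-post comparison with a declared direction, knowledge of phase can bias them, and no planned analysis would separate that bias from a treatment effect.

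Neither the size nor the presence of a bias can be derived from the documents, which give no session SD and no coder-error figure. The illustration shows only that a shift of a quarter to one session SD would be large on the scale of the planned effect size. It rests on the assumed shift, normal independent scores and the assumed 0.5 marker.

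It would also be wrong to infer that naming accuracy is fully protected: masking of the coders is not stated there either. The change should be made before outcome coding begins. Nothing in the point calls the treatment or the design as a whole into question.

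**What to change.** Add to section V.e:

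> For the outcome analysis, recordings and transcripts of pre- and post-treatment connected speech, and of naming attempts used for feature-word counts, will have date, phase and session labels removed, be placed in random order, and be coded in that order for object words, feature words and CIUs by existing study staff, where possible not the clinician who treated that participant. Naming accuracy needed during the study for eligibility, object selection and the stopping criterion will still be scored at the time. Participants without recordings will be identified as coded unmasked.

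This also settles the Aim 1b question, because feature words in naming attempts are named explicitly.

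The cost is file relabelling and a shuffled coding list, with no additional staff. Connected-speech and feature-word coding must wait until a participant's sessions are complete. Speech content may still give the phase away, so the risk falls but does not vanish.

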b. Study endpoints. The participant's participation with the study will end when they request to withdraw from the study, or after the post-treatment assessments have been completed, whichever occurs first.

c. Statistical methods.

We will use visual inspection⁶⁸, mixed-effects modeling, and effect size calculations to analyze all results. For visual inspection, we will use the conservative dual-criterion method^{20,27,82}. We will use mixed-effects modeling to estimate the extent to which treatment-specific factors (fixed effects), pre-treatment cognitive-linguistic measures (random effects), and participant-specific factors (random effects) explain post-treatment naming and connected speech outcomes. We will calculate effect sizes by subtracting a participant's average pre-treatment score from their average post-treatment score and dividing by the pre-treatment standard deviation⁸.

Aim 1a. Measure PWAs' naming accuracy for trained and untrained objects. We will calculate effect sizes to measure the effect of treatment on participants' naming accuracy for trained objects, untrained semantically-related objects, and untrained semantically-unrelated objects between pre- and post-treatment. Hypotheses: Consistent with prior studies, we expect that naming treatment will yield medium to large effects for trained objects. Additionally, we hypothesize that strategy training will result in an increase in circumlocution-facilitated naming for untrained unrelated objects and yield medium effects for all untrained objects, regardless of semantic relatedness.

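### The assessments that select the naming objects are also their only baseline, so the dual-criterion method will signal naming gains too often; the weekly probe count is given as both seven and eight

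*Combined protocol and SAP*

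**What the plan says.** On the schedule, V.a step 2 gives the treatment length: "Participants will attend three 70-minute treatment sessions per week for eight consecutive weeks". It then places the probes: "Starting on Week 2, the first treatment session of each week will begin with a 30-minute assessment". The Aim 1b analysis in VI.c follows strategy knowledge "from Treatment Week 2, to Week 8, to post-treatment sessions". V.e (during-treatment data) says instead: "These weekly probes will occur once per week for the eight weeks of treatment". The series can also end early: "Treatment will stop at the end of the eight weeks, or after three consecutive naming probe performances over 90% accuracy, whichever occurs first".

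On the baseline, V.a Phase 1(b) has three pre-treatment administrations of the 176-item naming assessment, intended to give a stable baseline. The same three decide which objects are used: "Any objects a participant is unable to name on one, two, or three assessments will be included" in the participant's object list. The treatment and probe lists are drawn from those objects with regard to semantic category and complexity. List sizes are not given, and no test between selection and the start of treatment is described.

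On the rule, VI.c applies visual inspection, mixed models and effect sizes to all results, and for visual inspection says "we will use the conservative dual-criterion method". It does not state the line shift, the trend method, how many points must lie above the lines, or an error level.

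**The concern.** An object enters the list because it was failed at least once on the baseline assessments. Some of those failures are chance: objects the participant can name on some days but not others. When such objects are tested again they score higher on average, with no treatment at all. The reference for each naming series is therefore too low from the start. All participants receive the same treatment, so no control arm would show the drift.

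The conservative dual-criterion method counts treatment-phase points above two lines fitted to the baseline. If the baseline is biased low, both lines tend to sit too low and the count is too easily reached. At stake is whether a positive visual-inspection result on naming reflects treatment or selection. The seven-or-eight question adds to this because the number of points fixes the count required.

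**Working it through.** **Probe count.** Weeks 2 to 8 give 8 - 2 + 1 = 7 probes (V.a; Aim 1b in VI.c). Once per week for eight weeks gives 8 (V.e). The plan states no error rate, so there is no such figure to reproduce.

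**Direction and size of the drift.** Let an object's naming probability p be constant over time. It is kept unless named on all three baselines, so P(kept) = 1 - E[p³]. Mean accuracy on kept objects is

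- on the selecting baselines: (E[p] - E[p³]) / (1 - E[p³]);
- on any later untreated test: (E[p] - E[p⁴]) / (1 - E[p³]).

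For p uniform on 0 to 1, E[p] = 1/2, E[p³] = 1/4 and E[p⁴] = 1/5. The baseline mean is 0.25/0.75 = 0.33 and the later mean is 0.30/0.75 = 0.40. Simulation gives the same two values.

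**Assumed decision rule.** Mean line and least-squares trend line through the baseline, each raised by 0.25 baseline SD; a point counts if it is above both. If the required count is set by a one-sided binomial with probability 1/2:

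- 7 of 7: 1/128 = 0.008
- 6 of 7: 8/128 = 0.0625
- 7 of 8: 9/256 = 0.035

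A 0.05 cut-off then requires 7 of 7 or 7 of 8. This cut-off is an assumption.

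**Simulation with no treatment effect.** 176 objects (V.a); p from Beta(1,1), Beta(0.5,0.5) or Beta(2,2); three baselines; objects failed at least once kept; probe list drawn at random from them; the same baselines used as reference; 4,000 participants per cell. Entries are the percentage of participants for whom an effect is indicated, as the range over the three distributions.

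| Probe objects | 7 of 7 | 6 of 7 | 7 of 8 |
|---|---|---|---|
| 16 | 7.0-7.6 | 17.8-18.3 | 14.5-15.4 |
| 20 | 8.0-8.8 | 19.2-20.8 | 16.9-17.7 |
| 40 | 12.2-14.0 | 26.2-29.2 | 24.6-25.9 |
| 80 | 23.4-24.0 | 39.7-41.8 | 35.8-38.0 |
| all kept | 31.0-36.9 | 48.4-53.1 | 45.3-52.1 |
| no selection effect (20-80, uniform p) | 1.7-1.9 | 5.5-6.3 | 4.1-5.0 |

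The standard error of an entry near 25% is √(0.25 × 0.75/4000) = 0.7 points. A repeat run gave 7-13% and 15-25% for 16-40 objects, and 23-36% and 37-50% for 80 or more (7 of 7 and 7 of 8).

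**Sensitivity.** Two distributions weighted to hard objects, Beta(0.3,0.5) and Beta(1,2), give less: 4-10% (7 of 7) and 9-19% (7 of 8) with 16-40 objects; 10-23% and 20-37% with 80 or more. A stationary normal series without selection, with lag-1 autocorrelation from 0 to 0.5, gives 1.6-5.4% and 4.3-8.7%.

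**With one untreated post-selection probe as a fourth baseline point**, seven treatment probes and 7 of 7 required (three main distributions): 2.9-3.5% with 16 objects, 3.7-4.8% with 20-40, and 5.7-7.1% with 80 or more.

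**The case against.** The strongest reply is that these rates are not properties of the plan. List size, object difficulty, line shift and required count are all assumed, and lists are drawn at random although the plan balances category and complexity. That stands: the figures are conditional. The direction does not depend on them, because some objects that are failed at times will be named at other times.

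A second reply is that the Aim 1a naming analysis specifies effect sizes, and visual inspection is written out only for strategy knowledge in Aim 1b, where object selection plays no part. That also limits the point. But VI.c names visual inspection for all results, and the effect size subtracts the same pre-treatment average, so it inherits the drift (not sized here).

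Some stronger readings are tempting but unsupported:

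- A reader might infer that choosing eight probes over seven roughly doubles the false-signal rate. That follows only from comparing 7 of 7 with 7 of 8. If 6 of 7 is accepted, seven probes signal more often than 7 of 8 in every row of the table.
- A reader might infer a responder rule run at a multiple of a nominal 5%. The documents define no responder and state no 5% level.
- A reader might take V.e to imply a pre-treatment Week 1 probe. It lists the weekly probes as during-treatment data, so that timing is a proposal.

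**Conclusion.** The count conflict is certain: seven by V.a and the Aim 1b analysis, eight by V.e. Taken alone it is minor.

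The more important fault is that selection and baseline share the same three assessments. If naming varies from one occasion to the next, this biases the naming reference low. Under the rule assumed above and the three main difficulty distributions, the dual-criterion method indicates an effect in untreated naming series several times as often as it would with a baseline free of selection, and more often the longer the probe list. Over every setting tried, including those weighted to hard objects, the range is about 4-37% for 7 of 7 and 9-52% for 7 of 8. Re-use of the selection assessments is the main cause; the probe count matters only through the cut-off chosen.

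The finding concerns naming probes. Connected speech involves no object selection and needs no change on this ground.

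**What to change.** 1. Reconcile V.a, V.e and VI.c. Hold the disputed Week 1 probe at the start of the first session, before any treatment, and count it as a post-selection baseline point for naming. State that the treatment phase has seven probes (Weeks 2-8), fewer if treatment stops early.
2. State the probe-list size, line shift, trend method and required count: 7 of 7 for seven probes, and the count for a shortened series. The stopping rule can be met by the third probe. On the binomial basis above, 3 of 3 has probability 1/8 = 0.125 and 4 of 4 has 1/16 = 0.0625, while 5 of 5 has 1/32 = 0.031. With fewer than five probes no count falls below 0.05, so the plan should say what is concluded then.
3. Report that some bias remains, since three of the four baseline points are still the selecting ones. If 6 of 7 were accepted, the rate with the added probe would still be about 9-14%.
4. For strategy knowledge, treat the Week 1 probe as a single untreated reference point. V.a describes no earlier strategy probe, and one point gives neither an SD nor a trend line.

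The cost is one probe of about 30 minutes per participant at a visit already scheduled, plus wording. The three session parts (15 + 40 + 15 = 70 minutes) already fill the session, so the probe either lengthens it or takes time from it.
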